20.3 Expected adverse events

For this trial, foreseeable adverse events include the following (including the need for hospital admission and/or further unplanned surgery to manage these complications in either group):

- (a) Complications related to the cast (including, but not limited to, pressure areas) or
- (b) Complications related to surgery (including, but not limited to: wound infection, nerve injury, wound healing problems (overgranulation, hypertrophic/keloid scarring), malunion, non-union, re-fracture or broken metalwork).

Planned surgery for the removal of metal pins/screws/ plates will be recorded as part of routine treatment and will not be regarded as a complication.

20.4 Reportable Aes/SAEs

Aes that are foreseeable in the treatment of these fractures do not need to be reported immediately, provided they are recorded in the Additional Care/Site Follow up Complication CRFs.

For the purpose of safety recording for this trial, only unexpected SAEs potentially related to the intervention will be reported to the central CTU study team.

IRAS ID: 324571 Page **30** of **50**

² Medical events that may jeopardise the participant or may require an intervention to prevent one of the above characteristics/consequences.

20.5 Non-reportable Aes/SAEs

Aes that are unrelated to the injury, intervention or treatment will not be reported. Aes deemed related to the intervention that do not meet the SAE definition and are not classed as foreseeable as per section 20.3 (such as tingling, pins and needles/discomfort, sensation of warmth/cold), will also not be reported.

20.6 Procedure for collecting safety events from sites/participants

These events will be recorded on patient-reported questionnaire (Additional Care) and by the site in the Site Follow Up Complications CRF if they become aware of such an event.

20.7 Reporting of SAEs from sites to the central CTU study team

Only SAEs considered by the PI to be related (possibly, probably, or definitely) to the study intervention/any of the research procedures will be reported immediately to the central CTU study team. Such events will be reported immediately to the central CTU study team as follows:

SAEs will be reported by the site research team using the SAE form within the REDCap study database within 24 hours of becoming aware of the event. The CTU is automatically notified of the SAE report through the database. A paper SAE form should be used as a back-up if the SAE form is not available electronically. This should be e-mailed to the central CTU study team within 24 hours of becoming aware of the event. The central CTU study team will acknowledge receipt of any SAEs reported via e-mail within one working day and provide the site with a unique SAE Log number.

Refer to section 20.5 for events that do not require reporting.

20.8 Assessment of SAEs by the Principal Investigator (or delegate)

The PI (or delegated individual) is responsible for assessing all reported SAEs for seriousness, causality and expectedness.

20.8.1 Relatedness/causality

The assessment of "relatedness" to the study intervention is the responsibility of the PI at site or an agreed designee according to the following definitions:

Relationship to intervention	Attribution (Causality)	Description
Unrelated	Unrelated	The AE is clearly NOT related
		to the intervention
	Unlikely	The AE is doubtfully related to
		the intervention
Related	Possible	The AE may be related to the
		intervention
	Probable	The AE is likely related to the
		intervention
	Definite	The AE is clearly related to the
		intervention

20.9 Review of SAEs by the Sponsor/CTU Nominated Person

An appropriately qualified person will review the SAE and raise any queries with the reporting site. If the site has not provided an assessment of causality and has not responded to the query, it will be assumed that the event reported is related to the study procedures/intervention. The site will be encouraged to respond and if a response is not provided the CI will be consulted by the CTU and the CTU will complete the Sponsor part of the SAE report.

20.10 Reporting of SAEs to the Research Ethics Committee (REC)

All intervention/study procedure **related** SAEs will be recorded and reported to the REC as part of the annual reports. All SAEs that are assessed as related and unexpected will be submitted to the REC within 15 days of the CTU/Sponsor becoming aware of the event. All such events will also be reported to the TMG, TSC and the Data Safety and Monitoring Committee (DSMC) at their next meetings.

20.11 Unblinding of SAEs for reporting to the REC

Not applicable. There is no blinding in this study.

20.12 Follow-up of Serious Adverse Events

If the SAE is an unexpected related event then follow-up information must be provided as requested by the central CTU study team. A follow-up report must be completed when the SAE resolves, is unlikely to change, or when additional information becomes available.

21 PREGNANCY

If a participant does become pregnant during their participation in the study, it does not need to be reported due to the nature of the intervention as per the risk assessment made regarding the study.

22 STATISTICAL CONSIDERATIONS

22.1 Statistical Analysis Plan (SAP)

The statistical aspects of the study are summarised here with details fully described in a separate SAP that will be drafted before the study opens and finalised prior to the final analysis data lock. The SAP will be written by the Study Statistician in accordance with the current OCTRU SOPs and will be finalised and agreed by the trial statistician, the CI and the TMG. The DSMC will review and, if necessary, provide input into the SAP.

22.2 Sample Size/Power calculations

172 participants providing data on the PROMIS Mobility Score for children at 24 months post-randomisation (86 in each group) will have 90% power to detect a difference in means of 5 assuming the SD is 10 using a two-group t-test with a 5% two-sided significance level. This is inflated to 192 patients (96 per arm) allowing for 10% attrition.

Raw scores of the PROMIS Mobility Score for Children are translated into standardised T-scores with a population mean of 50 and an SD of 10. The minimal clinically important difference (MCID) of PROMIS paediatric measures is generally 3.0-5.0 ^{27,28}.

We discussed with young people and families our experience from previous trials, in particular that families are reluctant to be randomised to surgery unless there is a marked improvement to be gained. Parents were extremely anxious about surgery, and we have learned their strong sense of responsibility when 'subjecting their child to surgery', believing the benefit must significantly outweigh the perceived risks. We therefore seek an effect size at the upper range of the MCID. Other studies have similarly highlighted that patients often seek greater effect sizes to warrant surgical interventions than the established MCID.²⁹

22.3 Description of Statistical Methods

Results will be reported in line with the Consolidated Standards of Reporting Trials (CONSORT) statement and any appropriate extensions and will be described fully in a separate SAP. A single final unblinded statistical analysis will take place after all follow-up has been completed, and sufficient time has been allowed for data collection and cleaning.

Standard descriptive statistics will be used to describe the demographics between the treatment groups reporting means and standard deviations (SD) or medians and interquartile ranges as appropriate for continuous variables and numbers and percentages for binary and categorical variables.

It is anticipated that all statistical analysis will be undertaken using Stata (StataCorp LP, www.stata.com) or other validated statistical software.

22.3.1 Primary outcome

The PROMIS Mobility Score for Children at 24 months is the primary outcome of the study and the primary analysis will compare the treatment groups in a linear mixed effects model including all patients, all time-points and adjusting for the stratification factors as fixed effects, with centre as a random effect. A treatment by time interaction will be included, and the model is anticipated to use an unstructured covariance matrix and restricted maximum likelihood. The analysis will adjust for the stratification factors (recommend by ICH-E9) - this will have a greater power to detect the minimum important difference than the unpaired t-test which was used for the power calculation ³⁰. A secondary analysis will compare treatment groups using analysis of covariance adjusted for baseline scores to explore consistency between the treatment effect. The adjusted mean difference between groups will be presented, together with 95% CI and p-values.

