15 RANDOMISATION

15.1 Timing of randomisation

The patient will be randomised after consent and baseline data have been obtained, either in the emergency department, or in a fracture clinic (face-to-face or virtual clinic- if virtual, site will inform the parent/guardian of the treatment allocation). All hospital treatment areas have access to the internet so will access the randomisation service in real time, i.e. there will be no delay to patient treatment.

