22.3.2 Secondary outcome(s)

Continuous secondary outcomes will be analysed using a mixed effects model as per the primary outcome, with model adjustment for baseline scores/values and stratification factors. These will be reported as an adjusted mean difference with 95% CIs and p-values. Binary outcomes will be reported in terms of relative and absolute risk, analysed using logistic regression adjusted for stratification factors.

The number of complications will be presented by treatment arm, and the proportion of participants who receive at least one complication will be analysed as a binary outcome.

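### The primary mixed model names no adjustment for baseline PROMIS-Mobility, although 22.3.2 adjusts the continuous secondary models for baseline; aligning the two would gain precision at no cost

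*Protocol*

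**What the plan says.** Section 22.3.1 describes the primary analysis of the 24-month score as a "linear mixed effects model including all patients, all time-points and adjusting for the stratification factors as fixed effects". Centre is a random effect, a treatment-by-time interaction is included, and an unstructured covariance with REML is anticipated. The stratification factors (10.1.2, 15.3) are sex, age group and emergency realignment, so baseline PROMIS-Mobility does not enter through them. It appears only later in 22.3.1: "A secondary analysis will compare treatment groups using analysis of covariance adjusted for baseline scores", to explore consistency.

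Section 22.3.2 says that continuous secondary outcomes follow the primary model, "with model adjustment for baseline scores/values and stratification factors". The table in 9.3 lists PROMIS-Mobility at 6 weeks and at 3, 6 and 12 months among these outcomes.

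The baseline score is a legitimate covariate. Section 10.1.2 lists it among the data collected after consent, and 15.1 states: "The patient will be randomised after consent and baseline data have been obtained".

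**The concern.** Read literally, the same instrument is adjusted for baseline up to 12 months but not at 24 months, where it is the primary endpoint. The other reading is that 22.3.2 takes the primary model to be baseline-adjusted already, and then it does not match the terms listed in 22.3.1. Either way, the text does not settle which model produces the headline estimate.

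Including all time-points does not settle it. If baseline is one of the responses and the treatment-by-time interaction is left free, the model fits a separate baseline mean in each arm. The 24-month contrast is then not corrected for any baseline difference. What is at stake is precision, and protection of the headline estimate against chance baseline imbalance, from data that are collected anyway.

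**Working it through.** **The plan's own figure.** Section 22.2 states that the trial "will have 90% power to detect a difference in means of 5 assuming the SD is 10". The method there is an unpaired t-test, two-sided at the 5% level, and the evaluable size is 86 per arm. The t-test requires 85.03 per arm, so 86 per arm and 172 in total; power at 86 per arm is 90.3%. Allowing for 10% attrition, 172 / 0.9 = 191.1, which becomes 192 at 96 per arm. The stated size reproduces, and it uses no baseline adjustment.

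**Effect of adjusting for baseline.** Let rho be the correlation between baseline and 24-month scores. The protocol gives no value, so the range below is assumed. The residual SD is 10 × sqrt(1 - rho²), and SE = residual SD × sqrt(2/86). The 95% half-width is 1.96 × SE. Power is from the same t-test with difference 5. The last column is 172/(1 - rho²) - 172, the extra evaluable participants that would give the same precision without adjustment.

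| rho | Residual SD | SE | 95% half-width | Power | Equivalent extra participants |
|---|---|---|---|---|---|
| 0 | 10.00 | 1.53 | 2.99 | 90.3% | 0 |
| 0.1 | 9.95 | 1.52 | 2.97 | 90.6% | about 2 |
| 0.2 | 9.80 | 1.49 | 2.93 | 91.4% | about 7 |
| 0.3 | 9.54 | 1.46 | 2.85 | 92.8% | about 17 |
| 0.4 | 9.17 | 1.40 | 2.74 | 94.5% | about 33 |
| 0.5 | 8.66 | 1.32 | 2.59 | 96.4% | about 57 |

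The SE falls by 0.5% at rho 0.1, 4.6% at rho 0.3 and 13.4% at rho 0.5.

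**Does including all time-points recover this?** The generalised least squares SE of the 24-month contrast was computed for the six time points (baseline to 24 months), with 96 per arm, SD 10 throughout and an assumed correlation of 0.5 among follow-up scores.

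| How baseline enters | Complete data, rho 0.3 | Complete data, rho 0.5 | About 10% missing at 24 months, rho 0.3 |
|---|---|---|---|
| Left out | 1.443 | 1.443 | 1.493 |
| Response, free treatment-by-time | 1.443 | 1.443 | 1.492 |
| Response, arm means equal at baseline | 1.377 | 1.250 | 1.428 |
| Covariate | 1.377 | 1.250 | 1.428 |

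The complete-data figures can be checked by hand: 10 × sqrt(2/96) = 1.443; 1.443 × sqrt(0.91) = 1.377; 1.443 × sqrt(0.75) = 1.250. A free baseline response is no better than leaving baseline out. A covariate and a constrained response give the same gain.

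**Chance imbalance.** If the baseline SD is also 10 (an assumption, since 22.2 gives 10 for the reference population and for planning), the between-arm baseline difference has SD 10 × sqrt(2/96) = 1.44 points. At rho 0.3, an imbalance of one SD moves the unadjusted 24-month estimate by 0.3 × 1.44 = 0.43 points, about 9% of the 5-point target.

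**The case against.** Four points can be made for the plan as written.

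- **How baseline is coded is often settled in the SAP**, and 22.1 and 22.3 defer detail to one. This holds in part. But 22.3.1 goes beyond deferral: it lists the model's terms and places baseline adjustment in a secondary analysis. A SAP that follows it would inherit the less precise primary model.
- **The wording is ambiguous rather than a clear omission.** This stands. A reader might infer that the protocol definitely excludes baseline from the primary model. Section 22.3.2 ties the secondary models to the primary one and can be read as implying adjustment in both, so the supportable point is that the sections disagree or are unclear.
- **A baseline-adjusted estimate will be reported anyway, through the ANCOVA.** This is true, and it would make an imbalance visible. It does not change which estimate is the headline.
- **Baseline may predict little.** It is taken within 7 days of a displaced fracture (11.4), with the limb temporarily immobilised (section 13). A low correlation with function two years later is plausible, although this is inference and not a figure in the protocol. Sex, age group and realignment are already in the model, so the relevant rho is what remains after them. At rho 0.2 the gain is 1.1 percentage points of power.

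A reader might also infer that every secondary model is baseline-adjusted. The protocol does not say so: binary outcomes are adjusted for the stratification factors only. Cosmesis, satisfaction, educational participation and leg length have no baseline value in 9.3 or Tables 2 and 3.

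**Conclusion.** The point holds as a free improvement. Section 22.3.1 names no baseline adjustment in the primary model, 22.3.2 applies it to continuous secondary outcomes that have a baseline, and a free baseline response would not supply it.

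Two stronger conclusions are tempting and not supported. The primary analysis is not biased: under randomisation the unadjusted comparison is valid. The trial is not underpowered: the 90% was calculated without baseline adjustment and reproduces at 90.3%. Nor is the claim in 22.3.1 of more power than the t-test contradicted, because it is attributed to the stratification factors.

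What is given up is a factor of about sqrt(1 - rho²) in the SE. Over an assumed rho of 0.2 to 0.5, power at 86 per arm would be 91.4% to 96.4% instead of 90.3%, and the lower end may be the more realistic. These figures assume SD 10 at 24 months; the imbalance figure also assumes a baseline SD of 10.

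**What to change.** In 22.3.1, state that the primary model adjusts for baseline PROMIS-Mobility in one of two ways:

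- the baseline T-score as a fixed covariate with its interaction with time, and 6 weeks to 24 months as the outcomes; or
- baseline as a response, with the arm means constrained equal at that time point.

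Keep the stratification factors and centre as they are, and keep the 24-month ANCOVA as a consistency check. Align 22.3.2 by saying that baseline adjustment applies to continuous outcomes that have a baseline measurement, and carry the same wording into the SAP.

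The cost is about one sentence in each document and a few degrees of freedom. No new data and no change in sample size are needed. The change should be made before any unblinded analysis, so that the choice cannot appear data-driven.

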22.3.2 Secondary outcome(s)

Continuous secondary outcomes will be analysed using a mixed effects model as per the primary outcome, with model adjustment for baseline scores/values and stratification factors. These will be reported as an adjusted mean difference with 95% CIs and p-values. Binary outcomes will be reported in terms of relative and absolute risk, analysed using logistic regression adjusted for stratification factors.

The number of complications will be presented by treatment arm, and the proportion of participants who receive at least one complication will be analysed as a binary outcome.

22.4 Inclusion in analysis

The principal analysis will be performed on the as randomised (ITT) population, analysing participants with available outcome data in their randomised groups, regardless of adherence or actual treatment received. The study will be reported in line with CONSORT guidelines.

22.5 Subgroup analysis

We will explore consistency of the primary treatment effect for important diagnostic subgroups. We will confirm the final subgroups in the SAP, but as a minimum, these will include the stratification factors sex, age (8-12 years and 13-15 years) and whether any emergency realignment was performed.

22.6 Interim analyses

The main outcomes will be analysed as stated in the analysis plan once the study follow-up has been completed. No formal interim analyses of treatment effect are planned for any of the study outcomes.

22.6.1 Stopping rules

As no formal interim analyses are planned, no stopping rules have been incorporated into the study design. An independent DSMC will review the accumulating data at regular intervals and may recommend pausing or stopping the study in the event of safety concerns.

Page **33** of **50**

IRAS ID: 324571

22.7 Level of Statistical Significance

All comparative outcomes will be presented as summary statistics and reported together with 95% confidence intervals and all tests will be carried out at a 5% two-sided significance level.

22.8 Procedure for accounting for missing data

The procedure for handling spurious or missing data will be described in the SAP. The study will attempt to collect data as completely as possible. The sample size calculation incorporated an inflation to account for potential loss to follow-up. The main analysis of the primary outcome will use a mixed model which will include all participants who have at least one set of outcome data.

22.9 Procedures for reporting any deviation(s) from the original statistical analysis plan Any deviation(s) from the original SAP will be described in the final statistical report.

22.10 Internal pilot/Decision Points

An internal pilot is planned that will progress seamlessly to the definitive study if predefined progression criteria are reached. Data from the internal pilot trial will contribute to the final analysis. The purpose of the internal pilot is to determine the number of eligible patients recruited to each centre and assess the rate at which recruitment progresses and to optimise the procedures for recruitment.

Stop-go criteria decisions will be determined with the oversight committee and funder after 9 months of recruitment.

The TMG will closely monitor the progression criteria during the internal pilot, and together with the TSC and DSMC will perform a full review towards the end of the internal pilot. The TSC and funder would make the final decision to terminate the study.

The internal pilot study will mirror the procedures and logistics undertaken in the main definitive study. It is intended that the study will progress seamlessly into the main phase, with internal pilot participants included in the final analysis. Should a decision be made to stop the study, participants will be followed up as per protocol.

23 HEALTH ECONOMICS

We have integrated an economic evaluation, informed by the NICE Reference Case³¹ and reported according to the Consolidated Health Economic Evaluation Reporting Standards statement ³². The economic evaluation will be conducted from the perspective of the UK NHS and Personal Social Services. A Health Economics Analysis Plan, providing full details of the prospective economic analysis, will be finalised before the end of follow-up.

Participant's use of primary, secondary and community care services, as well as medications will be collected using an electronic resource use questionnaire ³³. The resource use questionnaire will be designed with note to the relevance of information and the complexity of the task. Unit costs will be applied to resource use using national reference sources.

Health status will be determined using the EQ-5D-Y questionnaire, with utilities derived based on the UK adult tariff, or an age-specific valuation set if this becomes available. Quality-adjusted life-years (QALYs) will then be calculated using an area under the curve approach. Missing data will be managed following best practice, and imputation will be considered to avoid the potential bias of complete case analysis.

Costs and QALYs will be discounted at the recommended rate and adjusted for any baseline difference using regression models ^{34,35}. The primary economic outcome will be the incremental cost-effectiveness ratio expressed as the incremental cost per QALY gained. Uncertainty in costs and QALYs

will be assessed using bootstrap credible intervals, with the probability of cost-effectiveness at different willingness to pay threshold values represented using cost-effectiveness acceptability curves. Economic outcomes from the trial will be used to parameterise a decision analytic model, which will be used to assess future costs and benefits. Parameters which cannot be derived from within the trial will be sought from the wider literature. Uncertainties in parameter inputs will be accounted for with parametric distributions for each point estimate. This will enable probabilistic sensitivity analyses to be performed using Monte Carlo simulation.

From a broader socioeconomic perspective, out-of-pocket expenses and workdays missed by parents/carers because of their child's condition, and time off school will be recorded and reported.

